1.3 Rationale for the Proposed Study

Metastatic CRC is the second leading cause of cancer death in the US, accounting for nearly 50,000 deaths each year. Approximately 95% of patients with metastatic CRC have pMMR disease, and are in need of new therapies with manageable side-effects which can produce durable treatment responses, as has been observed with pembrolizumab monotherapy in patients with MSI-H/dMMR CRC[8]. First- and second-line standard of care regimens for metastatic CRC are FOLFOX and 5-FU, leucovorin, and irinotecan (FOLFIRI) with or without a biologic agent (bevacizumab or, if RAS wild-type, an epidermal growth factor receptor [EGFR]-targeted antibody). Recently US Food and Drug Administration (FDA)-approved third-line therapies are regorafenib and TAS-102. Regorafenib was approved based on a median OS of 6.4 months compared to 5 months with placebo and is associated with a median PFS of 2 months and objective response rate (ORR) of 1% [35]. TAS-102 was approved based on a median OS of 7.1 months, versus 5.3 months with placebo; with a median PFS of 2 months and ORR of 1.6% [23].

Patients with resectable liver metastases have a chance for cure with metastasectomy. Perioperative chemotherapy is standard of care in such cases, with a goal to eliminate any extra-hepatic micrometastatic disease [6]. FOLFOX (or CapeOx) is the preferred preoperative *Phase 2, Pembrolizumab, Vactosertib*

chemotherapy regimen in patients with resectable metastatic disease at diagnosis (synnorous metastases), as it is associated with reversible morbidity (sinusoidal injury) without increased mortality. By contrast, the other first-line chemotherapy regimen, FOLFIRI, is associated with increased mortality related to steatohepatitis (especially in high-risk populations or with extended resections)[6, 24]. Moreover, the addition of biologics to chemotherapy in the context of (potentially) resectable metastatic CRC remains uncertain, with agents such as cetuximab not clearly demonstrating benefit in this setting [25]. Bevacizumab is also typically not used in this context, as it should be stopped at least a month prior to surgery to avoid bleeding or wound healing complications. Additionally, there is evidence that once started bevacizumab should be continued even beyond progression [26].

As in the Nordlinger study, we typically give 6 cycles of FOLFOX to patients with synchronous metastases who are candidates for liver resection [6]. Practice patterns vary greatly for patients with metachronous metastatic disease, based on the specific circumstances, hence flexibly was built into this protocol for feasibility. When applicable, it is then standard to wait 4 to 8 weeks from the time of last FOLFOX administration until surgery. This waiting period represents a window of opportunity to intervene.

Additionally, only about 30% of patients with hepatic metastases treated with curative intent actually achieve cure [2, 27]. Most recurrences occur within 2 years of surgery, so 2-year relapse-free survival (RFS) is a common intervention endpoint [28, 29]. Importantly, despite the high recurrence rate, observation is recommended after surgery for resectable metastases in patients who have received prior oxaliplatin-based therapy because no standard chemotherapy has been proven to improve RFS [30]. Introduction of experimental adjuvant therapy after metastasectomy offers another opportunity for intervention, with a goal to clear any remaining micrometastatic disease.

1.3.1 Rationale for Perioperative Pembrolizumab-Based Treatment

Identification of new strategies to augment immune-related responses in the broader population of metastatic CRC patients, without dMMR or MSI-H tumors, is essential[31]. Whereas immune checkpoint inhibitors such as pembrolizumab have shown robust single-agent antitumor activity in the ~5% of patients with metastatic CRCs harboring MSI-H or dMMR, novel strategies are needed for the ~95% of patients with MSS or pMMR metastatic CRC [8]. These strategies may include combining pembrolizumab with cytotoxic, targeted, or other immunotherapy agents.

Potentially resectable metastatic CRC represents an ideal clinical setting to assess both the clinical efficacy and immunologic/pharmacodynamics effects of pembrolizumab-based therapies, as the majority of carefully selected patients are ultimately taken to surgery following preoperative therapy (87.3% in the Nordlinger EORTC study)[6]; therefore, a large quantity of tumor tissue is available for immune cell characterization and immune/molecular profiling.

The Primary Objective of this study is to characterize change in the populations of TILs induced by neoadjuvant pembrolizumab-based therapy in patients with metastatic CRC with potentially resectable hepatic metastases. The Primary Endpoint is specifically defined as the proportion of patients with a ≥ 2 -fold increase in the TILs in post- vs. pre-pembrolizumab-based treatment tumor specimens. A ≥ 2 fold increase was the threshold used for 2 prior trials of neoadjuvant immunotherapy [28, 29]. Including a prospective study evaluating the direct immune effects of sipuleucel-T on prostate cancer tissue in the peri-operative setting. Sipuleucel-T, which was FDA-

approved for improved OS in prostate cancer, induced a >2 fold increase in TILs per unit area of tissue [28]. We believe that a doubling in immune infiltration would be deemed as biologic meaningful, whereas magnitudes of change less than that can be more arguable for publication. In two published trials of prostate cancer we have shown that neoadjuvant immunotherapies can induce a >3x increase in TILs[36]. This is in excess of the doubling with which we set the threshold in this trial.

This concept is part of a larger collaboration between UCSF and Merck to dissect the changes within the tumor microenvironment induced with pembrolizumab-based combinations in 3 distinct indications (non-small cell lung cancer [NSCLC], RCC, and CRC). The combinations and cohorts that will move forward will be selected by a Joint Steering Committee (JSC) comprised of both UCSF and Merck researchers. We anticipate flexibility in the design to “go where the science takes us.” Thus, patient accruals may ultimately shift between the indications.

The Secondary Objectives of this study are to establish the safety/toxicity profile and explore the efficacy of pembrolizumab + vactosertib in patients with CRC with potentially resectable hepatic metastases. The following outcomes will be measured: adverse events (AEs) and perioperative complications, pathologic response, R0 resection rate, and 2-year RFS. Two-year RFS rates will be compared between participants who do and do not receive adjuvant pembrolizumab-based therapy.

While the current protocol focuses on pembrolizumab + vactosertib following chemotherapy, we anticipate exploring other novel pembrolizumab-based combinations during this same post-chemotherapy/preoperative window (e.g., pembrolizumab in combination with other immuno- or molecularly targeted agents following FOLFOX). These novel combinations will be incorporated into the study as protocol amendments, and patients will be enrolled to them in a sequential, non-randomized fashion.

1.3.2 Rationale for Dose Regimen

The planned dose of pembrolizumab for this study is 200 mg (IV) for 1 neoadjuvant cycle and 400 mg (IV) for up to eight 6-week adjuvant cycles (optional). The pembrolizumab doses used in this trial have been demonstrated to be well tolerated in earlier clinical trials.

The planned dose of vactosertib for this study is 200 mg PO QD, 5 days per week for 2 weeks during the neoadjuvant treatment period, and 200 mg PO QD, 5 days per week for 6 weeks (1 cycle) and depending on tolerability, patients will receive 200 mg PO BID, 5 days per week for up to 42 weeks (7 cycles) during the optional adjuvant treatment period. The vactosertib dosing regimen used in this trial has been demonstrated to be well tolerated in the ongoing early phase clinical trials.

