- Participants who meet study eligibility criteria (Section 3.3) and have adequately recovered from toxicity or complications of a surgery or other procedure, per the assessment of the treating investigator will be offered participation in the adjuvant treatment cohort (pembrolizumab plus vactosertib). Patients who still have their primary tumor in place (i.e. not surgically removed) would not be eligible for the optional adjuvant treatment.
- If the participant meets all other eligibility criteria to receive pembrolizumab plus vactosertib (e.g., no safety issues), then they will receive adjuvant treatment 6 weeks (± 2 weeks) after hepatic metastasectomy. Participants will receive adjuvant pembrolizumab plus vactosertib for up to eight 6-week cycles (approximately 1 year) or until disease progression is radiographically documented, unacceptable adverse event(s), intercurrent illness that prevents further administration of treatment, investigator's decision to discontinue the patient, administrative reasons requiring cessation of treatment, or withdrawal of consent, whichever occurs first.
- Correlative labs will be performed every 12 weeks during the adjuvant treatment period.
- Participants will be followed for up to 1 year after the last dose of pembrolizumab is administered, or until disease progression, the start of new anticancer treatment, or withdrawal of consent, whichever occurs first.

List of Abbreviations

5-FU	5-fuorouracil
AE	adverse event
ALP	alkaline phosphatase
ALT	alanine aminotransferase
ANC	Absolute neutrophil count
AST	aspartate aminotransferase
BID	twice a day (bis in die)
CBC	complete blood cell (count)
CD	Cluster of differentiation
CEA	Carcinoembryonic antigen
CNB	core needle biopsy
CR	complete response
CRC	Colorectal cancer
CrCl	creatinine clearance
CRF	case report form
CT	computerized tomography
CTCEA	Common Terminology Criteria for Adverse Events
CTLA-4	cytotoxic T-lymphocyte-associated protein 4
CTMS	Clinical Trial Management System
dMMR	Mismatch repair deficient
DSMC	Data and Safety Monitoring Committee
DSMP	Data and Safety Monitoring Plan
ECI	events of clinical interest
ECOG	Eastern Cooperative Oncology Group
EGFR	Epidermal growth factor receptor
ELISA	enzyme-linked immunoassay
EORTC	European Organisation for Research and Treatment of Cancer
EPO	Erythropoietin
ERC	Ethics Review Committee
FDA	United States Food and Drug Administration
FFPE	Formalin-fixed paraffin-embedded

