5.1.1 Pembrolizumab

Pembrolizumab will be administered as a 30-minute IV infusion. Every effort will be made to target infusion timing to be as close to 30 minutes as possible. However, given the variability of infusion pumps, a window of -5 minutes and +10 minutes is permitted (i.e. infusion time is 30 minutes: -5 min/+10 min). All IV infusion treatments will be administered on an outpatient basis.

Phase 2, Pembrolizumab, Vactosertib

Note: Treatment with pembrolizumab may be administered up to 3 days before or after the scheduled Day 1 of each cycle due to administrative reasons (such as holidays).

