5.3.3 Other Allowed Dose Interruption for Pembrolizumab

Pembrolizumab may be interrupted for situations other than treatment-related AEs such as medical or surgical events and/or unforeseen circumstances not related to study intervention. For patients who receive optional adjuvant therapy with pembrolizumab and vactosertib, pembrolizumab is to be restarted within 42 days (6 weeks) of the originally scheduled dose for Q6W dosing and within 84 days of the previously administered dose, unless otherwise discussed with Merck. The reason for study treatment interruption is to be documented in the patient's study record.

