- Obtain standard of care MSI/MMR and expanded RAS/BRAF mutation testing from liver resection specimen if not tested previously. Review pathology report.
- Baseline medications taken within 28 days of C1D1.
- Repeat liver biopsy if patient unable to undergo liver resection surgery.

- f. Stool collection at following time points ± 2 day window: mandatory collection post-chemo/ pre-C1D1 on day minus 4 and day minus 2, mandatory collection post-C1D1/ pre-surgery; optional at post-surgical follow-up.
- g. Review of baseline imaging to establish anticipated candidacy for liver resection.
- h. Baseline imaging should include a CT chest and IV contrast-enhanced CT or magnetic resonance imaging (MRI) abdomen/pelvis.
- i. Can be performed within 7 days prior to C1D1.
- j. Pembrolizumab will be administered at a fixed dose of 200 mg (IV) and vactosertib will be taken QD, PO 5 days per week C1D1 through C1D14 . See section 5.1.
- k. All participants will be followed for up to 1 year after the last dose of pembrolizumab is administered or up to 2 years after surgery whichever occurs last.
- l. Interested participants will complete the pre-treatment procedures outlined in Table 11 below and section 6.1.6.1.
- m. Participants who are not interested or are ineligible for the adjuvant treatment cohort will be followed Q90D ± 14 d post-surgery for up to 2 years as outlined in Table 10 and section 6.1.7.
- n. Can be performed within 10 days of C1D1
- o. Not needed for eligibility. Every effort should be made to collect archival tissue samples but if sample is not collected or unavailable it should not constitute a protocol deviation.
- p. For tumor marker assessments (CEA): record CEA at diagnosis, prior to and after lead-in FOLFOX/CapeOx

Table 11 Flow Chart for Adjuvant Treatment Cohort

Trial Period:	Pre-Treatment	Adjuvant Treatment				Post-Treatment		
		C1 D1	C2 D1	C3 D1	C4-8 D1	End of TX	Safety F/U	Follow Up Phase ^g
Scheduling Window:	2w ±14d post-op	6w ±14d post-op	12w ±3d post-op	18w ±3d post-op	24w-48w ±3d post-op	At DC +7d	30d after DC +7d	D90D ±14d post-last pembro dose for 1y or post-surgery for 2y (whichever occurs last)
Adjuvant TX Informed Consent	X							
Review of Eligibility ^a	X							
Disease Status Assessment/Measurable disease	X ^e							X
Tumor Imaging		X ^e		X ^e	X ^e	X		X
Concomitant Medication Review	X	X	X	X	X	X	X	X
Trial Treatment Administration ^f		X	X	X	X			
Dispense vactosertib		X	X	X	X			
Post-study anticancer therapy status								X

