- f. Pembrolizumab will be administered at a fixed dose of 400 mg (IV) Q6W and vactosertib will be taken PO 5 days per week. See section 5.1.
- g. Follow-up: every effort should be made to collect information regarding disease status for 1 year after last pembrolizumab dosing, progressive disease or death, whichever comes first. Follow-up assessments and subsequent anti-neoplastic therapy are at the discretion of the treating investigator. It is advised that patients should be assessed every 90 days (\pm 14 days) for 1 year after liver resection surgery by radiologic CT imaging with IV contrast to monitor disease status. Additional post-operative chemotherapy will be at the discretion of the treating physician. Information regarding post-study anti-neoplastic treatment will be collected if such treatment is initiated. Safety labs and correlative labs will be collected up to 1 year post-pembrolizumab.

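### Table 11 times adjuvant Cycles 2 to 8 from surgery (±3 days) while Cycle 1 may move by ±14 days, so the first two adjuvant doses can fall 25 to 59 days apart in a 6-week regimen

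*Combined protocol and SAP*

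**What the plan says.** **Cycle length.** Section 1.3.2 describes pembrolizumab as "200 mg (IV) for 1 neoadjuvant cycle and 400 mg (IV) for up to eight 6-week adjuvant cycles (optional" and the first adjuvant cycle of vactosertib as "200 mg PO QD, 5 days per week for 6 weeks (1 cycle". Table 5 gives pembrolizumab every 6 weeks. Sections 3.4 and 6.1.6.2 speak of eight 6-week cycles. Footnote f of Table 11 repeats it: "Pembrolizumab will be administered at a fixed dose of 400 mg (IV) Q6W".

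**Start of adjuvant treatment.** The optional adjuvant part of the study schema says of eligible participants that "they will receive adjuvant treatment 6 weeks (± 2 weeks) after hepatic metastasectomy". Section 6.1.6.2 and the Table 11 header give the same window.

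**Later cycles.** The Table 11 header also dates Cycles 2 to 8 from surgery: Cycle 2 at 12 weeks and Cycle 3 at 18 weeks, each ±3 days, and Cycles 4 to 8 at "24w-48w ±3d post-op".

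**Which text governs.** Section 5.1 tells the site to give treatment when the flow charts say, so Table 11 is operative text. The same section contains Table 5, with its 6-week frequency.

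**Tolerances.** Section 5.1.1 says: "Treatment with pembrolizumab may be administered up to 3 days before or after the scheduled Day 1 of each cycle". It limits this to administrative reasons and does not say what the scheduled day is counted from. For interruptions, Section 5.3.3 says "pembrolizumab is to be restarted within 42 days (6 weeks) of the originally scheduled dose for Q6W dosing" and within 84 days of the previous dose. Both are upper limits.

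**The concern.** Table 11 lets the first adjuvant dose move by up to two weeks either way but does not let the second move with it. A patient who starts at week 8 is due Cycle 2 about four weeks later by the header, and six weeks later by footnote f of the same table. For many permitted start dates, no Cycle 2 date satisfies both rules.

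Two things are at stake. The first is the interval between 400 mg doses. The second is the vactosertib step-up. Section 1.2.2.3 explains that a lower starting dose was adopted after 4 of 11 patients needed dose adjustment or withdrawal, and that a once-daily first cycle is meant to let tolerability develop before the dose rises. Sections 1.3.2 and 5.1.2 make the twice-daily dose from Cycle 2 depend on how Cycle 1 was tolerated. If the header governs, the length of that observation period depends on when the patient happened to start, and adverse events reported by cycle refer to unequal exposure times.

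**Working it through.** **Inputs, in days after surgery**

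| Item | Source | Days |
|---|---|---|
| Cycle 1 Day 1 | Table 11; schema; 6.1.6.2 | 42 ± 14 = 28 to 56 |
| Cycle 2 Day 1 | Table 11 | 84 ± 3 = 81 to 87 |
| Cycle 3 Day 1 | Table 11 | 126 ± 3 |
| Cycle 8 Day 1 | Table 11 | 336 ± 3 |
| Cycle length | 1.3.2; Table 5; 6.1.6.2; footnote f | 42 |

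**1. The plan's own figure.** At nominal dates the table agrees with the text: 84 − 42 = 42 days between Cycles 1 and 2, and 6 weeks + 7 × 6 weeks = 48 weeks for Cycle 8. The conflict comes from the windows alone.

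**2. Interval from Cycle 1 to Cycle 2 under the header**
- Shortest: earliest Cycle 2 − latest Cycle 1 = 81 − 56 = 25 days.
- Longest: latest Cycle 2 − earliest Cycle 1 = 87 − 28 = 59 days.

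Later pairs of cycles have ±3 days at each end, giving 42 − 6 = 36 to 42 + 6 = 48 days. Only the first interval is badly affected.

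**3. Can both rules be met?** Let *d* be the actual Cycle 1 day. Counting 42 ± 3 days from it puts Cycle 2 on days *d* + 39 to *d* + 45. That range meets days 81 to 87 only if *d* + 45 ≥ 81 and *d* + 39 ≤ 87, so 36 ≤ *d* ≤ 48.
- Permitted start dates: 56 − 28 + 1 = 29.
- Dates on which both rules can be met: 48 − 36 + 1 = 13.
- Dates on which they cannot: days 28 to 35 (8) and 49 to 56 (8), 16 in all.

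At the extremes, a day-28 start puts Cycle 2 on days 67 to 73 and a day-56 start on days 95 to 101. Both lie outside the Table 11 window.

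**4. Later cycles.** With exact 42-day cycles, Cycle 8 falls on day *d* + 7 × 42 = *d* + 294. That is day 322 for *d* = 28 and day 350 for *d* = 56, against a window of 333 to 339. The mismatch therefore concerns the header entries for Cycles 2 to 8, not Cycle 2 alone.

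**5. Once-daily vactosertib doses in Cycle 1,** at 5 days on and 2 off from Day 1, with Cycle 1 ending the day before Cycle 2 and no interruption:
- 42 days = 6 full weeks: 6 × 5 = 30 doses.
- 25 days = 3 full weeks + 4 days: 3 × 5 + 4 = 19 doses.

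**The case against.** The best defence is that the header row is only a nominal calendar. Its entries are what a start at exactly 6 weeks produces. The 6-week interval appears in many other places, Section 6.1.6.2 ties only the start of adjuvant treatment to surgery, and Section 5.3.3 measures interruptions from scheduled or previous doses. On that view a sensible site counts six weeks from the actual Cycle 1 date and never sees a 25-day interval. This is plausible, but no section says it. The header carries explicit ±3-day windows, and Section 5.1 sends the site to the flow charts. Counting from Cycle 1 also breaches the Cycle 2 window whenever Cycle 1 moves by more than 6 days.

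Several limits on the point do stand, and a reader might otherwise infer more than the documents support:
- **Share of patients.** The 16 of 29 dates are calendar dates weighted equally. The documents give no distribution of start dates, so this does not mean that about 55% of patients are affected. The count also uses ±3 days around a Cycle 1 anchor, whereas Section 5.1.1 offers ±3 days for administrative reasons and names no anchor.
- **The long end.** Section 5.3.3 tolerates up to 84 days between doses after an interruption, so 59 days is not outside what the protocol accepts elsewhere.
- **Slow recovery.** One might suppose that late starters are patients recovering slowly from surgery, so that the shortest interval falls on them. Adequate recovery is a condition for adjuvant treatment, but no section says that slow recovery is what drives late starts.
- **Automatic escalation.** A short Cycle 1 does not force a dose increase. Sections 5.1.2 and 5.2 make it depend on observed toxicity and the investigator's judgement.
- **Differences between sites.** This is a single-site trial, so inconsistent practice across sites is not an argument.
- **Scans, correlative blood and ECHO.** These are already keyed to cycle days and follow whichever Day 1 is used.

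**Conclusion.** The inconsistency is real. As written, Table 11 permits 25 to 59 days between the first two adjuvant doses of a regimen described throughout as 6-weekly. For Cycle 1 starts on days 28 to 35 or 49 to 56, the Table 11 window and a 42 ± 3 day interval from the actual start cannot both be met. The short end carries the weight: only upper limits on the interval are given, and the once-daily period before the escalation decision can shrink from 42 to 25 days.

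The 25-to-59 range assumes the header windows are followed literally, with no further allowance stacked on them. The 13-of-29 count assumes ±3 days around the actual Cycle 1 date. The dose counts assume uninterrupted 5-on, 2-off dosing.

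Severity is moderate. Only the optional adjuvant phase and its safety data are affected. The primary endpoint is measured from pre-treatment to surgery (Section 2.2), before any adjuvant dose; 2-year relapse-free survival runs from surgery (Section 7.1); and the secondary analyses are descriptive (Section 8.4.3). A reader might infer that the trial's main test, sample size or early stopping rule is compromised. None of these uses adjuvant cycle timing.

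**What to change.** Reconcile the Table 11 header windows for Cycles 2 to 8 with the 6-week statements in Section 1.3.2, Table 5, Section 6.1.6.2 and footnote f. State one time origin for Cycles 2 to 8, chosen so that the visit windows and the stated interval can both be met for every Cycle 1 date the protocol permits. In Section 5.1.1, say what the scheduled Day 1 is counted from. Which anchor and which interval limits are right is for the sponsor to decide. The scan, correlative blood and ECHO rows need no separate origin, since they are defined by cycle day.

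The cost is a wording change to one table header and one sentence at the next amendment, with no added patients, visits or procedures.
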